Full study protocol and statistical analysis plan

Official Title of the study:

An analysis soluble endoglin and matrix metalloproteinase 14 with Elisa method in the diagnosis and severity of early/late-onset preeclampsia

Date of the document:

June 2018.

Contents:

- 1. Participant Flow
- 2. Baseline Characteristics
- 3. Outcome Measures
- 4. Endpoints of the study
- 5. Limitations and Strengths
- 6. Certain Agreements
- 7. Results Point of Contact

1. Participant Flow

Recruitment Details

The study was conducted at Cengiz Gokcek Women's and Children's Hospital, Gaziantep, Turkey at department of obstetric and gynecology between date of January 2018 and December 2018. The study protocol was designed according to the Declaration of Helsinki, and the institutional ethical review board of Gaziantep University approved the study (Reference number: 2018/91). The study was conducted with 30 late-onset preeclampsia patients as group 1 (gestational age \geq 34 weeks), 33 patients with normal pregnancies as group 2 (gestational age \geq 34 weeks), 31 early-onset preeclampsia patients as group 3 (gestational age < 34 weeks), and 31 patients with normal pregnancies as group 4 (gestational age < 34 weeks). Finally, The authors consecutively recruited 61 pregnancies complicated with preeclampsia, and 64 healthy pregnancies will select for the control group. All participants included in the study gave oral and written informed consent.

Pre-assignment Details

The authors firstly were assessed the recruited people to ensure meeting the inclusion and

exclusion criteria.

The inclusion criteria were maken according to the official documents.

Arm/Group Information *

There are four groups in the study.

Arm/Group Title *

Preeclampsia groups = Group 1, group 3 Control groups= Group 2, group 4

2. Baseline Characteristics

In the analysis of variables, t-test was used for comparison of two groups and one-way analysis of variance was used for comparison of three groups. In addition, the demographic information of the variables were determined by frequency and percentage analyzes. The Statistical Package for the Social Sciences (IBM SPSS Statistics for Windows, Version 22.0,

IBM Corp., NY, USA).

3. Outcome Measures

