Every woman in the study population underwent obstetric ultrasound examination and fetal-maternal assessment was carried out by one of the authors. Obstetric anamneses were obtained from all subjects. The demographic data for gestational age, gravidity, parity, maternal age and BMI was recorded. Maternal venous blood samples were taken for measurement of serum MMP-14 and s-ENG levels after the diagnosis of early/late onset preeclampsia in outpatient clinic. These samples quickly centrifuged at 1,500 g for 10 min, plasma and serum samples were separated and serum samples were stored at -80 C until the day of measurement. The participants with early/late onset preeclampsia were hospitalized. In early onset preeclampsia, a betamethasone injection was administered immediately after hospitalization. The pregnancy was immediately terminated in emergencies arising from maternal or fetal causes. Otherwise, blood pressure was measured every four hours during periods of rest. Hypertension can be confirmed within a shorter interval in patients with blood pressure >110mm Hg diastolic and >160mm Hg systolic in order to give timely antihypertensive treatment. Delivery should be postponed for at least 24-48 hours if maternal/fetal status permit. A betamethasone injection for lung maturation (two dosages of 12 mg at 24 h intervals) was given within the said period. The control group's samples were obtained during routine obstetrical care examination in the third trimester of pregnancy. Then these pregnant women were followed-up until delivery. The participants with late onset preeclampsia (LOPE) were also hospitalized and terminated. The control groups' samples obtained during the routine obstetrical care examination in the third trimester of pregnancy. Then these pregnant women were followed-up until the delivery. Four groups compared in terms of maternal age, BMI, gravida, parity, week of gestation, systolic/diastolic blood pressure, total protein in spot urine sample, white blood cell (WBC) count, hemoglobin, platelet count, blood urea nitrogen, creatinine, liver function tests (AST, ALT), MMP-14, s-ENG, and infant weight at delivery. The s-ENG level was measured with a commercially avaliable ELISA kits which is produced to detect human s-ENG level with a high sensitivity and specificity (Rel Assay Diagnostics, Gaziantep, Turkey). The measurements were done in accordance with company's protocol. The kit uses Sandwich-ELISA principle. Serum MMP-14 levels were determined using a commercially available ELISA kit, the Human MMP14 ELISA Kit (Rel Assay Diagnostics, Gaziantep, Turkey),

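### Does comparing raw infant weight between the two groups below 34 weeks, with no size-for-week measure, make the plan wrong?

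*Combined protocol and SAP*

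**What the plan says.** All places are in the combined protocol and SAP.

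- **Groups (section 1, Participant Flow).** Group 3 is 31 early-onset cases and group 4 is 31 normal pregnancies, both below 34 weeks. The controls are described thus: "64 healthy pregnancies will select for the control group".
- **Timing for controls (section 3, Outcome Measures).** "The control group's samples were obtained during routine obstetrical care examination in the third trimester of pregnancy". The next sentence reads: "Then these pregnant women were followed-up until delivery".
- **Timing for early-onset cases (section 3).** Blood is taken after diagnosis, and the women are then hospitalized. "The pregnancy was immediately terminated in emergencies arising from maternal or fetal causes". Otherwise delivery is put off by one to two days or more where the state of mother and fetus allows.
- **Gestational age (section 3).** "The demographic data for gestational age, gravidity, parity, maternal age and BMI was recorded". Week of gestation also stands in the list of variables compared across the four groups, with no time point. The same list ends with "MMP-14, s-ENG, and infant weight at delivery".
- **Tests (section 2, Baseline Characteristics).** "t-test was used for comparison of two groups and one-way analysis of variance was used for comparison of three groups". No covariate, centile or z-score is named.
- **Endpoints (section 4).** Serum MMP-14 is primary and serum s-ENG is secondary, each with its relation to severity. Infant weight is neither.

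**The concern.** Infant weight is strongly tied to the week of birth. Two groups that share a gestational-age band look matched on it, and a reader may take a lower mean weight among the early-onset cases as evidence of poor growth.

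The shared band gives no such matching at birth. If it applied at delivery, all 31 normal pregnancies in group 4 would have ended before 34 weeks, which does not fit healthy women seen at a routine visit and followed to delivery. Cases and controls also reach delivery by different routes. With only unadjusted tests named, the comparison in grams cannot separate infants who were small for their week from infants who were born earlier. At stake would be a misread growth effect of preeclampsia.

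**Working it through.** **Step 1: inputs.** The documents give the group sizes, and these agree with the stated totals: 30 + 31 = 61 cases and 33 + 31 = 64 controls. They give no week of delivery, birth-weight SD, significance level, power or sample-size calculation. Every figure below beyond 31 v 31 therefore rests on an assumption.

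**Step 2: what the raw difference measures.** Let G be the gap in mean week of delivery, b the weight gain per week, and g the mean weight deficit at a given week. Then, with b equal in both groups:

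raw difference = b × G + g

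Both terms can follow from the disease, because preeclampsia can bring delivery forward. The sum is the total difference in infant weight between cases and controls, and that is what an unadjusted comparison estimates. It would be wrong only if the plan read it as g alone.

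**Step 3: how much mixing is possible.** Assume b = 200 g per week, a within-week SD of 500 g and a delivery-week SD of 1.5. The total SD is √(500² + (200 × 1.5)²) = √340,000 ≈ 583 g. Three scenarios are set to the same 400 g (20,000 simulated studies each, 31 v 31, two-sided 0.05):

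| Scenario | b × G + g | Raw-gram test rejects | z-score test rejects |
|---|---|---|---|
| 2-week gap, no growth deficit | 400 + 0 | 0.758 | 0.050 |
| 1-week gap, 0.4 SD deficit | 200 + 200 | 0.757 | 0.342 |
| No gap, 0.8 SD deficit | 0 + 400 | 0.759 | 0.873 |

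The raw test cannot tell these apart. But the rejections are not false positives: mean weight in grams does differ by 400 g in every row. The rows agree because the inputs were chosen to sum to 400, and the 0.050 holds because the chart is assumed correct. The figures also move widely with the assumptions. With a slope of 0.2 to 0.5 SD per week and no growth deficit, the chance of a significant raw difference is 12% to 50% for a one-week gap and 35% to 98% for two weeks.

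**Step 4: what a z-score would add.** For 31 v 31 (60 degrees of freedom), the 95% CI half-width is t(0.975, 60) × √(2/31) = 2.000 × 0.254 = 0.508 SD. Power is 80% at 0.723 SD and 90% at 0.837 SD, so only a large growth effect would show. If the groups deliver at different weeks, they also fall on different parts of the reference chart. A chart offset between them acts as a spurious effect: with no growth deficit, offsets of 0.2, 0.3 and 0.5 SD raise rejection from 0.05 to 0.121, 0.213 and 0.491. Conditioning on week of delivery also removes a possible effect of the disease, so the z-score answers a narrower question.

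**Step 5: does it reach anything the plan concludes?** Both endpoints in section 4 are serum markers, measured in samples taken at diagnosis or at the routine visit. Infant weight does not enter either of them. It is the last item of a long descriptive list, and no section states a growth hypothesis or a growth finding.

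**The case for a change.** The strongest reply is that the plan itself chose to compare infant weight, so its meaning ought to be clear, and that clarity is cheap. Women are already followed to delivery and weight is already taken there. One more field, week at delivery, would do, with infant sex if the chart is sex-specific. Listing week of gestation as a separate variable does not settle the matter. Its time point is not given, its place among the demographic data points towards sampling, and two separate unadjusted comparisons would not show size for week even if it meant delivery. Raw weight could be kept and the z-score simply placed beside it.

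The facts in this stand: the band does not fix week of delivery, the time point is missing, and no size-for-week measure is planned. The same holds for groups 1 and 2, where late-onset cases are hospitalized and delivered while controls are followed. What does not follow is an error. Stating the time point and showing delivery week beside weight would write down missing detail, and would leave the analysis as it is. The z-score would answer a question that the plan does not pose, at low precision and with dependence on the chosen chart. Whether that is worth having is a matter of preference.

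**Conclusion.** The concern does not hold. It is right that groups 3 and 4 may deliver at different weeks and that raw grams cannot be read as size for week. But the plan offers no such reading. The raw difference is a valid description of the total difference in a variable that is not an endpoint, and the MMP-14 and s-ENG analyses are unaffected. Following the plan as written gives no wrong result on this point.

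The size of the mixing cannot be derived from the documents: the gap, the slope and both SDs are assumed, and the illustrative rates run from 12% to 98% over gaps of one to two weeks. The conclusion does not depend on those values. It rests on infant weight staying a descriptive variable, as sections 3 and 4 have it, and would change if a report of the study claimed impaired growth from the comparison in grams.

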
according to the manufacturer's instructions. Human MMP-14 ELISA kit is based on the principle of biotin double antibody sandwich technology.

4. *Endpoints of the study:*

The primary endpoint in this analysis is to evaluate the value of serum matrix metalloproteinase-14 levels (ng/ml) in preeclampsia patients and also address its relationship with its severity.

The secondary endpoint in this analysis is to evaluate the value of serum soluble endoglin levels (ng/ml) in preeclampsia patients and also address its relationship with its severity.

5.Limitations and strengths:

The main limitation of our study is the small number of patients. We do not have prepregnancy BMI of patients and controls. Levels of s-ENG and MMP-14 could also be measured in different compartments such as placenta, umbilical cord serum and amniotic fluid.

As for the strengths of the study, none of the patients had any treatments for preeclampsia and active labor

6. Certain Agreements

The authors declare that they have no conflict of interest.

7. Results Point of Contact

Corresponding Author: [name], Cengiz Gokcek Public Hospital, Department of Obstetrics

and Gynecology, Gaziantep/Turkey, [contact]

Adress: [name]

GAZİANTEP

GSM: [contact]

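### The plan neither balances the four groups over ELISA plates nor masks the laboratory, and its t-test/ANOVA has no plate term, so plate differences could pass for group differences in both markers

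*Combined protocol and SAP*

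**What the plan says.** Section 4 makes serum MMP-14 the primary endpoint and serum s-ENG the secondary one. Both come from commercial ELISA kits run on serum kept frozen until assay (section 3).

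- **s-ENG (section 3):** "The measurements were done in accordance with company's protocol".
- **MMP-14 (section 3):** the level was determined with a kit "according to the manufacturer's instructions".
- **Analysis (section 2, Baseline Characteristics):** "t-test was used for comparison of two groups", with one-way analysis of variance for three groups. No covariate, block or batch factor is named.
- **Numbers (section 1):** "The study was conducted with 30 late-onset preeclampsia patients as group 1", "33 patients with normal pregnancies as group 2", "31 early-onset preeclampsia patients as group 3" and "31 patients with normal pregnancies as group 4".

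The document does not mention the number of plates or runs, plate capacity, replicates, control samples carried across plates, inter-assay CV, allocation of groups to plates, or masking of laboratory staff. Section 5 does not list assay variation among the limitations.

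**The concern.** ELISA readings can shift from plate to plate. If the groups are spread unevenly over plates, part of that shift enters the difference between group means. The stated test computes its standard error from variation between women within a group, so it does not allow for this extra component and rejects too often.

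Both endpoints rest wholly on these readings. Because the serum was frozen and assayed later, the laboratory can choose the running order, and nothing in the plan constrains that choice. If plate and group coincide completely, no later analysis can tell them apart.

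**Working it through.** **1. Number of samples.** From section 1: 30 + 33 + 31 + 31 = 125, which agrees with 61 cases + 64 controls = 125. The document gives no sample-size or power calculation to reproduce.

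**2. Number of plates.** Assumptions: 96 wells, 0 to 16 of them used for standards and blanks, and 1 or 2 wells per sample. Plates = ceil(125 / floor((96 − standard wells) / replicates)).

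- Single wells: capacity 96 down to 80, so 2 plates.
- Duplicate, 0 to 12 standard wells: capacity 48 down to 42, so 3 plates.
- Duplicate, 14 to 16 standard wells: capacity 41 or 40, so 4 plates.

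Even with no standards, 125 exceeds 96, so one plate per marker is not enough on this format.

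**3. Type I error without a plate term.** Assumptions: log-scale values with within-group SD s of 0.5 or 0.8; independent plate effects with SD equal to the between-plate CV (5, 10 or 15%). Let k be the sum over plates of the squared difference between the two groups' shares on that plate. Then

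type I error = 2 × [1 − Φ(1.96 / √(1 + k × CV² / (s² × (1/n₁ + 1/n₂))))].

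For group 3 v 4 (31 each), s² × 2/31 is 0.01613 at s = 0.5 and 0.04129 at s = 0.8.

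- *Balanced plates:* k = 0, so the error is 5%.
- *40-sample plates filled in group order:* plate 1 holds 30 of group 1 and 10 of group 2; plate 2 holds 23 of group 2 and 17 of group 3; plate 3 holds 14 of group 3 and 26 of group 4; plate 4 holds 5 of group 4. Then k = (17/31)² + (14/31 − 26/31)² + (5/31)² = 0.301 + 0.150 + 0.026 = 0.477.
- *Each group on its own plate:* k = 1 + 1 = 2.

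Example, group order, s = 0.5, CV 10%: 0.477 × 0.01 / 0.01613 = 0.296; 1.96 / √1.296 = 1.72; error 8.5%.

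| Layout, group 3 v 4 | s = 0.5; CV 5 / 10 / 15% | s = 0.8; CV 5 / 10 / 15% |
|---|---|---|
| Balanced | 5 / 5 / 5% | 5 / 5 / 5% |
| Group order, 40 per plate | 5.9 / 8.5 / 12.9% | 5.3 / 6.3 / 8.1% |
| One plate per group | 8.7 / 19.0 / 31.4% | 6.4 / 10.8 / 17.5% |

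For group 1 v 2 in the same group-order layout, the error is 6.8 / 12.2 / 20.3% at s = 0.5 and 5.7 / 7.8 / 11.4% at s = 0.8. With 80 single-well samples per plate in group order, groups 1 and 2 share a plate and there is no inflation. Group 3 v 4 then gives 6.1 / 9.4 / 14.8% and 5.4 / 6.7 / 8.9%.

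**4. What the fix does.** Simulation, 10,000 runs, two plates, fixed plate shift of 0.25, 0.5 or 1.0 within-plate SD, for 61 v 64, 30 v 33 and 31 v 31:

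- 50/50 split, no plate term: about 0.03 to 0.05, slightly conservative at the larger shifts.
- 50/50 split with a plate term: 0.048 to 0.058.
- 75/25 split, 31 v 31, no plate term: 0.07 / 0.15 / 0.39 at the three shifts.
- 75/25 split with a plate term, all three comparisons: 0.047 to 0.054.

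**The case against.** The strongest reply is that the plan is silent, and silence is not evidence of a fault. A reader might infer that the groups were unevenly spread over plates, or that staff knew the group of each sample. The documents say neither. They refer to kit instructions that are not reproduced. This stands, and the point is confined to a missing safeguard.

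A reader might also infer that cases and controls were run in separate batches, because "The authors consecutively recruited 61 pregnancies complicated with preeclampsia, and 64 healthy pregnancies will select for the control group" puts the controls in the future tense. That is too thin. The document mixes tenses throughout, section 3 describes control sampling in the past tense, and frozen storage fits one deferred assay campaign at least as well. Enrolment order would not give one plate per group either: section 1 describes the 61 cases as a single consecutive series within 2018, which would tend to mix early- and late-onset disease.

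It is also fair to say that the absent plate term is not in itself the cause of false positives, since with balanced plates the plain test does not exceed 5%. And every input except group size is assumed: well count, standards, replicates, CV, log-SD and layout. No figure can be put on the effect of masking.

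What the reply does not remove is that more than one plate is needed on an ordinary format, that nothing in the plan secures balance, and that partial imbalance is enough to inflate the error.

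**Conclusion.** The point holds as a gap in the plan, not as a demonstrated bias. Neither marker has a provision for balance over plates or for masking, and the stated analysis would not correct for an imbalance. For group 3 v 4 the type I error ranges from the nominal 5% with balanced plates to 31% in the worst case examined (each group on its own plate, CV 15%, log-SD 0.5). Filling plates in group order gives intermediate values of about 5 to 13%. The upper figures should not be read as an estimate for this study: they need complete confounding, which the documents do not show and which filling 40-sample plates in group order would not produce. The conclusion rests on the assumed 96-well format and the assumed CV and log-SD ranges. The change is worth making because it protects both endpoints at very little cost.

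**What to change.** Add to section 3, for both markers: coded samples are assigned to plates at random within group, so that each plate carries all four groups in about equal proportion, and the operator is masked to group. Add to the analysis text: plate is included as a factor in the MMP-14 and s-ENG comparisons.

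Balance is the essential part, because it is what prevents bias. With balance secured, the plate term mainly restores precision. It also corrects a partial imbalance, but it cannot rescue complete confounding.

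The document is dated June 2018 and recruitment is given as running to December 2018, so the layout may still have been open. If the assays are already run, report the plate-by-group layout for each marker, fit the plate term where groups overlap, and say plainly where they do not.

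Cost: a plate map, coded tubes and one model term. With 2 to 4 plates the term uses 1 to 3 degrees of freedom. No extra samples, kits or staff are needed.

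### The title asks a diagnostic question, but the plan names only tests of means; a significant t-test could pass for diagnostic value when discrimination is poor

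*Combined protocol and SAP*

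**What the plan says.** The document presents itself as both protocol and statistical analysis plan.

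- **Question.** The official title concerns two markers "in the diagnosis and severity of early/late-onset preeclampsia".
- **Endpoints (section 4).** The primary endpoint is "to evaluate the value of serum matrix metalloproteinase-14 levels (ng/ml) in preeclampsia patients" and the secondary is "to evaluate the value of serum soluble endoglin levels (ng/ml) in preeclampsia patients". Each adds the marker's relationship with severity. Neither names a measure.
- **Methods (section 2, Baseline Characteristics).** "t-test was used for comparison of two groups and one-way analysis of variance was used for comparison of three groups". Beyond these tests, only counts and percentages are planned, and those are for demographic data.
- **Comparisons (section 3, Outcome Measures).** "Four groups compared in terms of maternal age, BMI, gravida, parity, week of gestation", followed by a longer list that includes both markers. No test is named here.
- **Sampling (sections 1 and 3).** Blood is drawn from cases once preeclampsia has been diagnosed. For comparison, "64 healthy pregnancies will select for the control group".

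Nowhere is there a ROC curve, AUC, cut-off, predictive value, likelihood ratio or classification model. Sensitivity and specificity are mentioned once, as properties of the s-ENG assay kit.

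**The concern.** A t-test asks whether two group means differ. Diagnosis asks how well a marker value places an individual woman in the right group. The two can diverge: distributions that overlap heavily still give a small p-value once the groups are large enough to fix the means.

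Carried out as written, the plan yields p-values for mean differences and no figure for discrimination. With *diagnosis* in the title, a small p-value invites a claim of diagnostic usefulness that no planned estimate supports.

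A second limit comes from the design. Known cases set against healthy women are an easier contrast than the one faced in women with suspected disease. Even a correctly estimated AUC would be case-control discrimination, and the conclusion has to be worded accordingly.

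**Working it through.** The plan gives no power, alpha, SD or effect size, so it has no figure of its own to reproduce. The question is what a significant t-test would imply about discrimination at the planned sizes.

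**Inputs from section 1, Recruitment Details**
- Late onset: 30 cases (group 1) v 33 controls (group 2).
- Early onset: 31 cases (group 3) v 31 controls (group 4).
- The totals agree: 30 + 31 = 61 cases, 33 + 31 = 64 controls.

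**Assumptions not in the document:** two-sided alpha 0.05; marker values normal with the same SD in cases and controls.

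**Step 1. Smallest standardised difference reaching p = 0.05**, d = t(0.975, n1 + n2 − 2) × √(1/n1 + 1/n2)
- Late: 2.000 × 0.2523 = 0.504
- Early: 2.000 × 0.2540 = 0.508

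**Step 2. Convert to discrimination**, with AUC = Φ(d/√2) and sensitivity at 90% specificity = Φ(d − 1.282)
- Late: AUC = Φ(0.357) = 0.64; sensitivity = Φ(−0.777) = 0.22
- Early: AUC = Φ(0.359) = 0.64; sensitivity = Φ(−0.773) = 0.22

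**Step 3. Difference detectable with 80% power (noncentral t)**

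| Stratum | d | AUC | Sensitivity at 90% specificity |
|---|---|---|---|
| Late, 30 v 33 | 0.718 | 0.694 | 0.29 |
| Early, 31 v 31 | 0.723 | 0.695 | 0.29 |

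Read the other way, a true AUC of 0.70 is d = √2 × Φ⁻¹(0.70) = 0.742, and the t-test would then be significant about 82% of the time in either stratum. So significance at a modest AUC is the expected result here.

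**Step 4. Precision if the AUC were reported (Hanley-McNeil)**

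For A = 0.80: Q₁ = A/(2 − A) = 0.6667 and Q₂ = 2A²/(1 + A) = 0.7111.

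SE² = [A(1 − A) + (n1 − 1)(Q₁ − A²) + (n2 − 1)(Q₂ − A²)] / (n1·n2)
- Late: (0.16 + 29 × 0.0267 + 32 × 0.0711)/990 = 0.00324, so SE = 0.057
- Early: (0.16 + 30 × 0.0267 + 30 × 0.0711)/961 = 0.00322, so SE = 0.057

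95% CI in each stratum: 0.80 ± 1.96 × 0.057 = 0.69 to 0.91. At an AUC of 0.70 the same formula gives 0.57 to 0.83. The interval is therefore needed to interpret the estimate.

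**The case against.** The strongest reply is that diagnosis appears only in the title. The endpoint, with its unit of ng/ml, may use *value* to mean simply the measured level, and comparing means would then be a reasonable analysis. That reading is possible, but it leaves the title's question with no planned analysis at all. The mismatch moves elsewhere and is not resolved.

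Next, the test sentence sits under Baseline Characteristics and covers two or three groups while the study has four, so the marker analysis might be called under-specified. That is fair as far as it goes. Still, the sentence is introduced as applying to the variables in general, and no other inferential method appears anywhere.

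Third, an AUC of 0.64 belongs to a result exactly at p = 0.05 and does not predict what the study will find. This stands. The figure shows what significance fails to rule out, and the 80%-power figures show that the point is not confined to the boundary.

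Fourth, sensitivity at 90% specificity would be unstable, because the cut-off depends on roughly three of the 31 to 33 controls. This also stands. Simulating 31 v 31 under the normal model with a true AUC of 0.80 gives a central 95% range of about 0.23 to 0.77 for the estimated sensitivity and 0.74 to 0.96 for the true specificity of the cut-off. It is a reason to show the interval and to put the AUC first.

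Finally, an AUC against healthy controls does not repair the choice of comparison group, nor does it answer the severity part of the endpoints. Both are correct: the first needs careful wording, and the second is a separate matter.

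**Conclusion.** The concern holds. The title poses a diagnostic question and the named methods cannot answer it. At the study's own sizes, a significant t-test is compatible with an AUC as low as 0.64 (22% sensitivity at 90% specificity), and 80% power is reached at an AUC of 0.69 to 0.70.

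Those figures rest on two-sided alpha 0.05 and equal-variance normality; skewed marker levels or unequal spread would change them. The main conclusion does not depend on them, since a test of means does not estimate discrimination under any distribution. The data remain usable and the gap is easily closed, so this is a change the sponsor should make and not a fatal flaw.

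**What to change.** Amend the analysis plan as follows.

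- For each marker, make the diagnostic analysis the AUC with 95% CI, separately for early onset (group 3 v 4) and late onset (group 1 v 2).
- Add sensitivity at a specificity fixed in advance, for example 90%, with a CI that reflects estimation of the cut-off from the controls. Fixing the specificity prevents choosing the most flattering cut-off after seeing the data.
- Do not pool the strata. The study set up gestational-age-specific controls, and a pooled AUC would describe neither form of the disease.
- Keep the comparison of means as supportive.
- Word the conclusion as discrimination of established preeclampsia from healthy pregnancy, not accuracy in women with suspected disease.

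If the sponsor does not want a discrimination analysis, the title and conclusions would have to be limited to differences in mean level.

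**Cost.** Plan wording and a standard ROC procedure on data already being collected; no extra participants, samples or assays. The price is wide intervals, especially for sensitivity, and a more modest claim.
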